5 TRIAL DELAY DISCOUNTING

You will now complete a series of decision-making tasks. You will be asked to make choices between different amounts of money given to you now or after a delay. These are hypothetical choices, but please choose your answer as if the items were to be delivered as described. Each task will start with some brief instructions on the screen. Read these instructions and press the 5 key on the keyboard when you are ready to begin. There are no right or wrong answers in the tasks, just choose which option you prefer in each case. Please take your time and answer thoughtfully. To select the option on the left side of the screen, press the left arrow, and to select the option on the right side of the screen, press the right arrow.

[Task implemented on computer via REDCap]

IN SESSION MEASURES (Administered after each cigarette)

Product Evaluation Scale

Think about your general experience when using the product you just tried.

Please answer the following questions about the product using the scale below [7-point scale, Not at all – Extremely]

Cigarette Product Code: _____	
1. Was it satisfying?	_____
2. Did it taste good?	_____
3. Did it make you dizzy?	_____
4. Did it calm you down?	_____
5. Did it help you concentrate?	_____
6. Did it make you feel more awake?	_____
7. Did it reduce your hunger for food?	_____
8. Did it make you nauseated?	_____
9. Did it make you feel less irritable?	_____
10. Did you enjoy the sensations in your mouth?	_____
11. Did it immediately reduce your craving for a cigarette?	_____
12. Did it relieve withdrawal symptoms?	_____
13. Did it relieve the urge to smoke?	_____
14. Was it enough nicotine?	_____
15. Was it too much nicotine?	_____
16. Was it easy to use?	_____

Roswell Park Protocol Number: I 757820

17. Were there bothersome side effects? _____

18. Would you be comfortable using the product in public? _____

19. Did you still have a craving for a cigarette after using the product? _____

20. Are you concerned you would become dependent on the product? _____

21. Did you enjoy using the product? _____

22. Would you be willing to use the product long term? _____

JUSTER PURCHASE INTENTION

How likely are you to purchase the product you just tried in the next month?

- 10 = Certain, practically certain
- 9 = Almost sure
- 8 = Very probable
- 7 = Probable
- 6 = Good possibility
- 5 = Fairly good possibility
- 4 = Fair possibility
- 3 = Some possibility
- 2 = Slight possibility

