- 1 = Very slight possibility
- 0 = No chance, almost no chance

Duke Cigarette Sensory Evaluation | 1-7 Not at all – Extremely|

[figure not shown]
Please rate the puffs you just took. Circle the number that best answers each question.

1. How much did you like the puffs you just took?
2. How satisfying were the puffs you just took?
3. How high in nicotine do you think the puffs were?
4. How similar to your own brand were the puffs?

Using the same scale as above, rate how strong the puffs were in the following places.

Roswell Park Protocol Number: I 757820

5. Strength of puffs on tongue?
6. Strength of puffs in nose?
7. Strength of puffs in back of mouth & throat?
8. Strength of puffs in windpipe?
9. Strength of puffs in chest?

[figure not shown]

Roswell Park Protocol Number: I 757820

DRUG EFFECTS / LIKING SCALE

Place a vertical line at the point on the scale that indicates how you feel about each of the statements right now.

1. Do you feel any study product effects?
2. Do you feel any good study product effects?
3. Do you feel any bad study product effects?
4. How much do you like the study product?
5. How much do you desire the study product?
6. How much would you like to use this product again?

Roswell Park Protocol Number: I 757820

HEDONIC ATTRIBUTE PROFILE

Draw	1 TOO EASY	2	3	4 JUST RIGHT	5	6	7 TOO HARD
Mouthful of Smoke	1	2	3	4	5	6	7
	TOO LITTLE			JUST RIGHT			TOO MUCH
Impact	1 TOO LITTLE	2	3	4 JUST RIGHT	5	6	7 TOO MUCH
Irritation	1 TOO LITTLE	2	3	4 JUST RIGHT	5	6	7 TOO MUCH
Strength	1 TOO MILD	2	3	4 JUST RIGHT	5	6	7 TOO STRONG
Smoothness	1 TOO SMOOTH	2	3	4 JUST RIGHT	5	6	7 TOO HARSH
Tobacco Taste	1 TOO LITTLE	2	3	4 JUST RIGHT	5	6	7 TOO MUCH
Tobacco Taste	1 UNPLEASANT	2	3	4 NEUTRAL	5	6	7 PLEASANT
Overall Taste	1 UNPLEASANT	2	3	4 NEUTRAL	5	6	7 PLEASANT
Aftertaste	1 UNPLEASANT	2	3	4 NEUTRAL	5	6	7 PLEASANT
Similarity to Usual brand	1 VERY DIFFERENT	2	3	4	5	6	7 VERY SIMILAR

Roswell Park Protocol Number: I 757820

PANAS (10 item) [1-5 Not at all – Extremely]

The next part involves a number of words that describe different feelings and emotions. I'll say each word, and you can indicate to what extent you feel this way RIGHT NOW, on a scale from 1-5. 1 means you don't feel this way at all or slightly feel this way right now. 2 means feeling this way a little, 3 means moderately, 4 means quite a bit, and 5 means extremely feeling this way right now.

1. Inspired
2. Afraid
3. Alert
4. Upset
5. Excited
6. Nervous
7. Enthusiastic
8. Scared

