This message:
Discourages me wanting to smoke
Makes smoking seem unpleasant to me
Makes me concerned about health effects of smoking

Negative Affect

How much did the label make you feel:
Anxious
Sad
Scared
Guilty
Disgusted

Roswell Park Protocol Number: I 757820

Thinking of Harms

How much did the labels make you think about:
The chemicals in the smoke of the cigarettes
Health problems caused by smoking
The harm your smoking might be doing to you
The harm your smoking might be doing to other people

Would you support or oppose a policy that required this label to appear on cigarette packages?
Strongly oppose – Strongly support

Would you support or oppose a policy that required this label to appear in advertising for cigarettes?
Strongly oppose – Strongly support

Remote Data Collection – EMA Schedule and Questionnaires

3 Daily Reports – 11 am, 4pm, 9pm (assessments < 5min)

How many cigarettes have you smoked since the last prompt?

How many of these cigarettes were research cigarettes?

How many of these cigarettes were not research cigarettes?

How you used any other tobacco products since the last prompt?

If yes: What product? How many times did you use it?

Please record your product weight with the provided scale.

RIGHT NOW: How would you rate your (0 – 100 VAS):

- Craving
- Irritability
- Anxiousness/nervousness
- Difficulty Concentrating
- Stress
- Bored
- Calm/Relaxed
- Happy
- Alert
- Enthusiastic

Provide Reminder to collect all cigarette butts in provided materials, store used pods

11 am Only (additional questions)

Hedonic Attribute Profile: In the past day, how would you rate the research cigarettes (1-7 Likert)

Draw

Irritation

Smoothness

Roswell Park Protocol Number: I 757820

Strength

Tobacco Taste

Similarity to Usual Brand

Product Evaluation Scale (1 - 7 Likert):

Was it satisfying?

Did it taste good?

Did it calm you down?

Did you enjoy the sensations in your mouth?

Did it reduce your craving for a cigarette?

Were there bothersome side effects?

Did you enjoy using the product?

Would you be willing to use the product long term?

Record CO measurement

9pm Only (additional questions):

Record CO measurement

Reflect on today as a whole: How would you rate your (0 – 100 VAS)

- Craving
- Irritability
- Anxiousness/nervousness
- Difficulty Concentrating
- Stress
- Bored
- Calm/Relaxed
- Happy
- Alert
- Enthusiastic

Thinking of the cigarettes you smoked today: How would you rate (0 – 100 VAS)

- Tastes like my own brand

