- Satisfying like my own brand
- Enjoyable like my own brand
- Relieved my cravings like my own brand

2-3 Pseudo-Random Prompts: Between 11 - 4, 4 – 9

Take picture of research cigarette pack

How often did you notice your warning label in the past day?

Have you read or looked closely at the warning label in the past day?

Have you made any effort to avoid looking at or thinking about the warning labels (such as covering them up, keeping them out of site, using a cigarette case, etc.)

Has seeing the warning label stopped you from having a cigarette when you were about to smoke?

Has seeing the warning label affected how you smoke a cigarette?

Has seeing the warning label affected how you hold a cigarette?

Roswell Park Protocol Number: I 757820

Think back on the most recent cigarette you smoked:

Where were you (home, work, other's home, vehicle, bar/restaurant outside, other)

Was smoking permitted (yes, discouraged, no)

Were you with others (yes, no)

- IF YES: Were they: smoking, vaping, both, neither

What activity were you doing (working/chores, inactive/leisure, socializing, eating/drinking, other)

How strong was your craving prior to use?

How many puffs did you take?

Duke Sensory Evaluation (1 – 7 Not at all – Extremely)

- How much did you like the puffs you took?
- How satisfying were the puffs you took?
- How high in nicotine do you think the puffs were?
- How similar to your own brand were the puffs?

Roswell Park Protocol Number: I 757820

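### The EMA Duke items, part of a first-primary instrument, neither limit the rating to research cigarettes nor record which cigarette was rated, so ratings of other cigarettes can dilute the message contrast.

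*Combined protocol and SAP*

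**What the plan says.** Section 3 lists the Duke Sensory Scale among the product-evaluation questionnaires of the first primary endpoint. The schedule in section 5.1 places these questionnaires at all three video sessions and, as selected items, in the daily EMA. Section 11.4 puts the Duke scale at the 1:30pm and 6:30pm prompts; Appendix C puts it at the pseudo-random prompts.

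The wording in Appendix C differs from block to block:

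- **Duke prompt.** The stem is "Think back on the most recent cigarette you smoked", followed after some context questions by items such as "How much did you like the puffs you took".
- **9pm report.** The stem is "Thinking of the cigarettes you smoked today: How would you rate". Section 11.4 describes these ratings equally broadly.
- **11am report.** The stem is "In the past day, how would you rate the research cigarettes", which is limited to study product.
- **Daily reports at 11am, 4pm and 9pm.** Research cigarettes are counted, and then "How many of these cigarettes were not research cigarettes".
- **Session form of the Duke scale.** The instruction is "Please rate the puffs you just took", under a heading for in-session use after each cigarette.

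Section 22.1 models EMA data with terms for message, sex and other-tobacco stratum. It does not say how a rating of a non-research cigarette is handled.

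**The concern.** Section 1.2 predicts that pack messages lower cigarette satisfaction. To test that for the labelled product, the rating has to be of the labelled product, or the analyst has to know when it was not. At the Duke prompt neither holds. A participant whose last cigarette was the usual brand rates the usual brand, including its similarity to the usual brand, and the score is stored with the study-product scores.

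Such ratings bring the arms closer together if they carry no message effect. If a message also leads some participants back to their own brand, and they like it better, the message arms gain high scores for a reason that is itself a sign of lost appeal. The contrast would then understate the effect.

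The session forms raise a related difficulty. They ask about puffs just taken and a product just tried, but the Session 2 and 3 descriptions in section 11.3 contain only questionnaires and, at Session 3, the return of materials.

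**Working it through.** The plan states no figure on this point, so there is none to reproduce. The check is of the text first, then of scale.

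**1. Which blocks name the study product?** The 11am Hedonic stem does, and the 11am Product Evaluation items follow in the same block. The Drug Effects items also refer to the study product. The Duke prompt and the 9pm stem do not. Only the Duke scale links this wording to a named primary instrument, because the 9pm comparisons with the own brand are not listed in section 3.

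**2. Is non-research smoking expected?** Yes. It is counted at each daily report, and section 22.1 plans to explore message condition against product compliance.

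**3. Can the rated cigarette be recovered?** In part. If the interval around a Duke prompt contains only research cigarettes, the rated one was a research cigarette; if it contains none, it was not. A mixed interval leaves it open. Also, the count question in Appendix C runs back to the preceding prompt, and the Duke prompt listed there has no count. Coverage of the stretch just before a Duke rating therefore depends on how participants read that question.

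**4. Does the model separate the ratings?** No. The other-tobacco stratum concerns dual use, not the brand of cigarette rated.

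**5. Scale (all inputs assumed).** Let f_c and f_m be the own-brand shares of rated cigarettes in the control and message arms, e the true message effect on the research-cigarette rating, and d the own-brand mean minus the control-arm research-cigarette mean. Assume the message does not alter own-brand ratings. Measured from the control-arm research-cigarette mean:

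- control arm = f_c × d
- message arm = (1 − f_m) × e + f_m × d
- observed difference = (1 − f_m) × e + (f_m − f_c) × d

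*Equal shares f.* The second term vanishes and the observed effect is (1 − f) × e. At f = 10% the loss is 10%; at 20% it is 20%. For an endpoint with 80% power at two-sided 0.008 (the plan gives no power for the Duke scale), power becomes Φ((1 − f) × (2.652 + 0.842) − 2.652), which is 69% at f = 10% and 56% at f = 20%.

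*Unequal shares, e = −0.5 on the 1–7 scale:*

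- f_c = 5%, f_m = 15%, d = 1.0: 0.85 × (−0.5) + 0.10 × 1.0 = −0.325, a 35% loss.
- f_c = 10%, f_m = 25%, d = 1.0: 0.75 × (−0.5) + 0.15 × 1.0 = −0.225, a 55% loss.
- f_c = 10%, f_m = 25%, d = 1.5: −0.375 + 0.225 = −0.15, a 70% loss.
- Shares reversed (25% and 10%), d = 1.5: 0.90 × (−0.5) − 0.15 × 1.5 = −0.675, an overstatement of 35%.

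The last line shows that the direction, as well as the size, depends on inputs the documents do not give.

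**The case against.** The best case for the plan is that exposure is narrow and already mitigated. Appendix D tells participants to use only the supplied cigarettes. Section 11.3 ties supply to usual consumption, and section 11.2 matches menthol preference. The Duke prompt itself opens with a photograph of the research pack and questions about its label, which puts the study product in mind. EMA carries four Duke items against nine in the session form, and nothing says the EMA items define the primary endpoint. Asking about whatever was smoked also answers a fair question about the effect of assignment.

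Much of this stands. It lowers the likely share of own-brand ratings, and it is a reason to keep every rating in the analysis. It does not close the gap: the form still counts departures, the photograph shows possession of a pack rather than the cigarette rated, and rounding supply to the nearest pack can leave it below usual consumption. The session data are not a clean substitute while Sessions 2 and 3 lack a usable referent.

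Three stronger readings are tempting, and the documents do not support them:

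- A reader might infer that the 9pm ratings also contaminate a primary endpoint. They share the loose wording but are not a named primary instrument.
- A reader might infer that the mixing cannot be undone. Intervals with one cigarette type can be resolved from the planned counts.
- A reader might take the 35% to 70% losses as an estimate. They rest wholly on assumed shares and rating gaps.

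Nor is Session 1 at fault in design: section 11.3 already has those scales rate the usual brand.

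**Conclusion.** The point holds for the EMA Duke items. Their wording admits any cigarette, the rated cigarette is not recorded, and no analysis rule deals with it. The result is a possible dilution of one component of the first primary endpoint. With equal shares the loss equals the own-brand share, assuming own-brand ratings carry no message effect; if the message lowers those ratings too, less is lost. A larger loss requires more own-brand use in the message arms together with a better-liked own brand. That is plausible, but nothing in the documents shows it. The wording defect is certain and its size is unknown. The point is a cheap improvement and does not invalidate the endpoint.

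**What to change.** - **Duke prompt.** Add one yes/no item: *Was your most recent cigarette a research cigarette?* The context questions can then still refer to any cigarette.
- **Analysis (section 22.1).** Analyse all ratings, and prespecify a further analysis limited to research-cigarette ratings. Report non-research use by arm beside it, because that restriction conditions on behaviour after randomisation and cannot stand alone. State whether session or EMA Duke data define the primary endpoint.
- **9pm stem.** Say research cigarettes, in both Appendix C and section 11.4.
- **Sessions 2 and 3.** Replace the references to puffs just taken and a product just tried with the research cigarettes smoked since the last session. At Session 1, only the form wording needs to match the usual-brand referent in section 11.3.

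The cost is one extra item per Duke prompt, a few words in the REDCap forms and a small departure from the original scale wording. If the forms can no longer be changed, classify Duke ratings by the interval counts, treat mixed intervals as unresolved, and present this as a sensitivity analysis.

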Appendix D: Experimenter Guide

1. Welcome and Introductions:

2. Introduction:

- I would appreciate if you can minimize distractions until our videoconference is done. If something important requires your attention, please let me know and we can take a brief pause.
- First, I'll ask you to complete an online questionnaire. Here, we are looking for some information about you and your tobacco use.
- We will then move onto training you on study procedures.
- There is no right or wrong answer here. You are the expert and we are really interested in your honest responses to questions and to the tasks during the laboratory session.
- Do you have any questions?

*Answer any questions.

3. Baseline Questionnaires

- "We will now begin the baseline questionnaires."
 - Baseline measures and covariates will assess:
 - Demographics (age, sex, race/ethnicity, education, income)
 - Tobacco use behaviors (consumption, brand, menthol preference, quit history)
 - Cognitive and affective measures
 - A series of previously used items will assess knowledge and perceptions of filter vents.^{113,117}
 - Nicotine dependence will be assessed using:
 - Fagerström Test for Nicotine Dependence (FTND;¹¹⁸)
 - Behavioral aspects of cigarette dependence will be assessed using:
 - The Glover-Nilsson scale^{120,121}
 - Questionnaires on vent messages
 - Questionnaires on message perceptions

We will now train you and provide you with supplies for the field study

Field Study Description

For the field study, you are going to use your mobile device to record your cigarette and other tobacco use and answer questions about how you're feeling and the situations in which you use your products. You will be prompted 5 times each day via text message to answer questionnaires. Three of these prompts will be at the same time every day: 11am, 4pm, and 9pm. Two of these prompts will be at a random time each day, one between 11am – 4pm and one between 4pm – 9pm. To receive bonus payment for the field study, you will need to respond to

Roswell Park Protocol Number: I 757820

all 5 prompts. If you fail to respond to prompts for 3 consecutive days, we will send you a warning. If compliance to procedures does not improve, you will be discontinued from the study.

Please keep track of the amount of cigarettes and other tobacco you use. The scheduled prompts will ask you to report the number of cigarettes you've smoked. The random prompts will ask you to report on the situation in which you last used your product, such as the location and if smoking was allowed. We also ask that you store all used cigarette butts in the provided materials

Here are examples of the questions you will be asked at each assessment (show questionnaires). Do you have any questions?

We are also providing you with a CO monitor that will connect with your phone to take a CO measurement each night (demonstrate use).

We are also providing you with a scale to weigh other tobacco products that you may use, such as an e-cigarette or smokeless tobacco. If you use these other products, we would like you to weigh your product (e.g., pod, tank, dip tin) at the beginning and end of each day. If you are close to finishing your product and may start a new one, please weigh both the older and newer one at the beginning and end of the day.

Two additional times during the field study, we will ask you to videoconference with us as a study check-in and to have you respond to some questionnaires.

These are the cigarettes we are asking you to use during the field study (provide research cigarettes). Please use only these cigarettes and do not tamper with the cigarette pack. At random points in the study, we may ask you to take a picture of the cigarette pack.

Do you understand the procedures for the field study? Please call us if you have any questions.

Videoconferencing Sessions 2 & 3

Hello, today we are going to have you fill out a questionnaire. I will send it to you now. Have you been regularly storing your cigarette butts. Can I see how you are storing them?

Compliance: Your compliance has been great. Thank you!

Or: Your compliance has not met the standards. Please respond to more prompts or you may be discontinued for the study. Do you have any questions about the study procedures that may help you respond to more prompts?

Session 3 only:

Please pack up your supplies to prepare a return shipment. Can I see how you've stored your supplies in the box?

When we receive your materials, we will send you payment for completing the study. Thank you for participating.

Roswell Park Protocol Number: I 757820

Ads for the website/mobile app:

RESEARCH PARTICIPANTS NEEDED

Searching for:
21-69 year old daily cigarette smokers
to participate in a 2 week field study

Participants will be compensated for their time

